# 10.2.5. Classification of Adverse Event Intensity and Relationship to Investigational Product

The severity of AEs or SAEs will be in accordance with the National Cancer Institute Common Terminology Criteria for Adverse Events (CTCAE version 5.0). A physician-investigator must make an assessment of severity. For those not listed in the CTCAE, the following criteria will be used:

**Mild:** An event that is usually transient, requiring no special treatment, and does

not generally interfere with the subject's daily activities.

**Moderate:** An event that interferes with usual activities of daily living, causing

discomfort but poses no significant or permanent risk of harm to the subject. The event is usually ameliorated with additional specific

therapeutic intervention.

**Severe:** An event that interrupts usual activities of daily living or significantly

affects clinical status. The event poses a significant risk of harm to the subject and hospitalization may be required, and typically requires

intensive therapeutic intervention.

The investigator must make an assessment of relationship to the investigational product based on the following criteria:

**Unrelated:** The subject did not receive the investigational product, the temporal sequence

of the AE/SAE onset relative to administration of the investigational product

is not reasonable, or there is another obvious cause of the AE/SAE.

**Unlikely:** There is evidence of exposure to the investigational product but there is

another more likely cause of the AE/SAE.

**Possible:** There is evidence of exposure to the investigational product, the temporal

sequence of the AE/SAE onset relative to administration of the investigational product is reasonable, but the AE/SAE could have been due to another equally

likely cause.

**Probable:** There is evidence of exposure to the investigational product, the temporal

sequence of the AE/SAE onset relative to administration of the investigational

product is reasonable, and the AE/SAE is more likely explained by the

investigational product than by any other cause.

**Definite** There is evidence of exposure to the investigational product, the temporal

sequence of the AE/SAE onset relative to administration of the investigational

product is reasonable, the AE/SAE is more likely explained by the

investigational product than by any other cause, and the AE/SAE shows a pattern consistent with previous knowledge of the investigational product or

investigational product class.

#### 10.2.6. Outcomes and Actions Taken

All unresolved AEs will be followed for a minimum of 7 days (unless the AE is an ongoing pregnancy which must be followed to conclusion) after the subject's final study visit, unless the investigator's judgment dictates otherwise, the event has resolved or stabilized prior to the 7-day period, or the subject is lost to follow-up.

Investigators are not obligated to actively seek AEs or SAEs in former study subjects that occur following the follow-up period.

For each recorded AE or SAE, the investigator must make an assessment of outcome at the time of last observation, as follows:

Oxytocin for Alcohol Use Disorder NCIG, NIAAA, NIH
Protocol Number: NCIG-007R

Fatal: The subject died.

Resolved without Sequelae: The AE or SAE has ended.

Resolved with Sequelae: The AE or SAE has ended but changes are noted from

baseline.

Unresolved – Ongoing: The AE has not ended and is ongoing at the end of the

reporting period (i.e., 7 days after the final Follow-up visit) and the investigator deems that further follow up is not medically

required

Unknown – Lost to Follow-up: Lost to follow-up after repeated unsuccessful attempts to

contact the subject.

Actions taken with respect to investigational agents (discontinuation or not) will also be recorded. In addition, if the AE was treated (medications or other physical measures), this will also be recorded.

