### 6.7. Investigational Product Administration

To control dosing and absorption of investigational product, subjects will be instructed to administer the nasal spray with their head in an upright position closing one nostril with one finger while administering the spray in the other nostril and sniffing during administration. At the first administration on Study Day 1, subjects will be provided with instruction on how to self-

administer their first dose, will be observed while administering the first dose, and will be given an instruction sheet to take home. At subsequent visits, subjects will be asked to return the nasal spray devices.

*Missed Doses:* Subjects will be instructed if the dose is not taken at the recommended time, to skip this dose, and the next dose should be taken at the time of next scheduled dose; doses should never be doubled up.

**Dose Reductions and Discontinuation.** If the subject is not tolerating the investigational product, the dose can be reduced by 14 IU or 200 μL increments per dose (2 less sprays) to determine if the subject can tolerate a lower dose. For example, one spray in each nostril can be omitted for each reduction. Then the subject should try to continue to give one dose in the morning and one dose in the evening if during the maintenance period. If the dose is reduced during the initial 2-week tolerability period, then subjects will not escalate to the maintenance dose and will stay at the tolerated dose. If the subject develops a medical condition requiring discontinuation of the investigational product, he/she can simply discontinue immediately. In the event that a female subject becomes pregnant, she will be instructed to discontinue taking the investigational product immediately.

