#### 7.14. Investigational Product Discontinuation

If the investigator determines that any study subject should discontinue taking investigational products, the subject should be told to discontinue taking the investigational products immediately. No dose reduction is necessary in this case. Subjects should continue in the study, even if withdrawn from investigational products, and complete all assessments. Dose reductions for intolerance are permitted (see section 6.7).

**Pregnancy.** Females who become pregnant during the course of the study will be instructed to discontinue use of the investigational product immediately. The investigator must report a pregnancy within 1 working day of the site being aware to the NIAAA Study Manager and the Medical Monitor.

**Physical Illness.** Subjects will need to be removed from investigational products if they have a serious illness or a disabling condition that precludes them from taking the investigational product.

**Adverse Events.** If the subject experiences any AEs that are considered study drug related and for which the investigator has determined that continuation of the study drug could be detrimental to the health of the subject, then drug will be immediately discontinued as described above.

**UPSIT Score.** If UPSIT score decreases to  $\leq 26$ , study drug will be discontinued but the subject should continue in the study and be monitored using the UPSIT to determine if this AE is reversible.

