# 10.31. Subject Disposition

A subject disposition eCRF will be completed for all subjects who are randomized to the study and who are dispensed investigational product. This eCRF will be used to record the following data as applicable: 1) completion status of the subject at the end of their participation and if they were discontinued early, and reason for early discontinuation.

Completion status is as follows:

- 1. Subject completed full study (i.e., telephone contact was made at the Week 14/15 follow-up).
- 2. Subject completed the full intervention phase of the study (i.e., subject came to Week 13 clinic visit during Week 13).
- 3. Subject was withdrawn prior to the Week 13 visit, but completed the end of study assessments scheduled at Week 13 (reasons for early withdrawal are to be specified).
- 4. Subject was withdrawn prior to the Week 13 visit and did not complete the end of study assessments (reasons for early withdrawal are to be specified).
- 5. Subject discontinued investigational products and the reason(s).

Even if the subject had investigational product suspended for any reason but attended clinic visits, the above definitions still apply.

In addition, if the subject was confined and/or incarcerated at any time during the study, the dates of confinement and/or incarceration will be collected.

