9.6 Safety Analysis

9.6.1 Adverse Events

AEs will be coded using the most recent version of the Medical Dictionary for Regulatory Activities (MedDRA) and will be grouped by system, organ, and class (SOC) and preferred term (PT) designation. The severity, frequency, and relationship of AEs to investigational product will be presented by SOC and PT groupings. Listings of each individual AE including start date, stop date, severity, relationship to IP, outcome, action taken (including any treatment administered), and duration will be provided.

Every AE will be assessed for whether or not it qualifies as an SAE. All SAEs will be categorized and listed according to the following categories: Congenital Anomaly or Birth Defect; Persistent or Significant Disability/Incapacity; Results in Death; Requires or Prolongs

Hospitalization; Other Medically Important Serious Event; or Life-Threatening. For deaths, the date and cause of death will be collected and listed. For hospitalizations, the dates of admission and release (discharge) will be collected and listed.

Each AE (based on PT) will be counted once only for a given study subject. If the same AE occurred on multiple occasions, the highest severity will be assumed. Thus, study subjects are not counted multiple times in a given numerator in the calculation of frequencies for a specific AE. C-SSRS reports of suicidality or suicidal ideation will be reported as AEs and analyzed as AEs if the investigator determines after an interview with the subject, that the responses are consistent with suicidal ideation or attempt. Tabulation of suicidal ideation by CSSRS will be presented without hypothesis testing; answers to the C-SSRS will be provided in a subject listing.

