Preferred Term	(N=xx)	(N=xx)
		I
SOC	nn (xx.x%)	nn (xx.x%)
- Overall -		
Preferred term 1	nn (xx.x%)	nn (xx.x%)
Preferred term 2	nn (xx.x%)	nn (xx.x%)
	nn (xx.x%)	nn (xx.x%)

Notes: Percentages are based on the total number of subjects, as given in the column heading.

Multiple occurrences of a specific adverse event for a subject are counted once in the frequency for the adverse event. Likewise, multiple occurrences of adverse events within a specific preferred term for a subject are counted once in the frequency for the preferred term.

Programmer's Notes: Order System Organ Class alphabetically and preferred term alphabetically within System Organ Class.

Table 100: Number and Percentage of Subjects with Adverse Events Leading to Discontinuation of Study Medication

MedDRA SOC/	Placebo	Oxytocin
Preferred Term	(N=xx)	(N=xx)
SOC	nn (xx.x%)	nn (xx.x%)
- Overall -		, , ,
Preferred term 1	nn (xx.x%)	nn (xx.x%)
Preferred term 2	nn (xx.x%)	nn (xx.x%)
	nn (xx.x%)	nn (xx.x%)

Multiple occurrences of a specific adverse event for a subject are counted once in the frequency for the adverse event. Likewise, multiple occurrences of adverse events within a specific preferred term for a subject are counted once in the frequency for the preferred term.

Programmer's Notes: Order System Organ Class alphabetically and preferred term alphabetically within System Organ Class.

Table 101: CIWA-AR Score ≥ 10 at Least Once During Treatment

							95%	CI
	Placebo	Oxytocin	Total					
	(N=xx)	(N=xx)	(N=xxx)	p-value ¹	Cohen's h	Odds Ratio	OR Lower CI	OR Upper CI
CIWA-AR Score >= 10								
Never	xx (xx.x%)	xx (xx.x%)	xx (xx.x%)					
At Least Once	xx (xx.x%)	xx (xx.x%)	xx (xx.x%)	0.xxx	0.xx	XX.XXX	XX.XXX	XX.XXX

1 Chi-squared test

Table 102: Summary of Vital Signs and Body Weights

Parameter	N	Mean	SD	Med	Max	Min
Vital Sign (units)						
Screening						
Placebo	XX	XX.X	XX.X	XX.X	XX.X	XX.X
Oxytocin	XX	XX.X	XX.X	XX.X	XX.X	XX.X
Week 1						
Placebo	XX	XX.X	XX.X	XX.X	XX.X	XX.X
Oxytocin	XX	XX.X	XX.X	XX.X	XX.X	XX.X
Change from baseline						
Placebo	XX	XX.X	XX.X	XX.X	XX.X	XX.X
Oxytocin	XX	XX.X	XX.X	XX.X	XX.X	XX.X
Weeks 1, 2, 3, 4, 6, 8, 10, 13						

Programmers note: vital signs include pulse rate, systolic blood pressure, and diastolic blood pressure. Body weight (lbs) will also be presented for screening, Weeks 6, 8, 10 and 13.

Table 103: Incidence of Abnormal Findings on Physical Exam in Nasal Mucosa

	Placebo	Oxytocin
	(N=xx)	(N=xx)
Abnomal Nasal Mucosa	nn (xx.x%)	nn (xx.x%)

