Subject ID	Group	Date	Week	Since your last visit did you attend any AA, 12-step, SOS, or similar group meeting?	How many?	Have you visited another health professional to get help reducing drinking?	What type of professional?
XXX	Oxytocin Placebo	mm/dd/yyyy	XX	Yes No	XXXX	Yes No	XXXXX

Listing 25: Drug Exposure

Subject ID No.	Treatment Group	Study Month	Date Start of Month	Date End of End of Month	Volume of Drug Prescribed	Volume of Drug Taken	Reason for Discontinuation
XXX	Oxytocin	1, 2, 3	mm/dd/yyyy	mm/dd/yyyy	xx	XX	
	Placebo						

Listing 26: Adverse Events

Subject ID	Treatment Group	Adverse Event (Verbatim) S: SOC P: PT Term	Start Date/ Day	Stop Date/ Day	Duration in Days	Severity	Relation -ship	Actions Taken	Outcome	Serious
XXX	Oxytocin	Verbatim	mm/dd/yyyy	mm/dd/yyyy		1	1	1	1	Yes
	Placebo	S: xxxx	XX	XX		2	2	2	2	No
		P: xxxx				3	3	3	3	
						4	4	4	4	
							5	5	5	
								6		

Severity: 1=Mild; 2=Moderate; 3=Severe; 4=Potentially Life-threatening. Relationship: 1= Unrelated; 2=Unlikely; 3=Possibly; 4=Probably; 5=Definitely

Action Taken Due to AE: 1=None; 2=Treated with Drugs; 3=Non-drug treatment; 4=ER/Outpatient visit; 5=Hospitalization; 6=Referral for treatment

Outcome: 1=Resolved; 2=Recovered with sequelae; 3=Ongoing; 4=Required treatment; 5=Unknown

Programmer's Note: If "Were any AEs reported?" checkbox=No, then display "None Reported" in the Adverse Event column and SOC/PT column. If an AE started and stopped the same day, the duration is 1 day.

Listing 27: Adverse Events Leading to Subject Discontinuation from Study

Subject ID	Treatment Group	Adverse Event (Verbatim) S: SOC P: PT Term	Start Date/ Day	Stop Date/ Day	Duration in Days	Severity	Relation -ship	Actions Taken	Outcome	Serious
XXX	Oxytocin	Verbatim	mm/dd/yyyy	mm/dd/yyyy		1	1	1	1	Yes
	Placebo	S: xxxx	XX	XX		2	2	2	2	No
		P: xxxx				3	3	3	3	
						4	4	4	4	
							5	5	5	
								6		

Severity: 1=Mild; 2=Moderate; 3=Severe; 4=Potentially Life-threatening. Relationship: 1= Unrelated; 2=Unlikely; 3=Possibly; 4=Probably; 5=Definitely

Action Taken Due to AE: 1=None; 2=Treated with Drugs; 3=Non-drug treatment; 4=ER/Outpatient visit; 5=Hospitalization; 6=Referral for treatment

Outcome: 1=Resolved; 2=Recovered with sequelae; 3=Ongoing; 4=Required treatment; 5=Unknown

Programmer's Note: If "Were any AEs reported?" checkbox=No, then display "None Reported" in the Adverse Event column and SOC/PT column. If an AE started and stopped the same day, the duration is 1 day.

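### Dose reductions for intolerance are allowed but never counted by arm, so tolerability is overstated to the extent that it is judged from discontinuations and compliance

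*Protocol*

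**What the plan says.** Protocol 6.7 makes reduction the response to intolerance: "If the subject is not tolerating the investigational product, the dose can be reduced by 14 IU" per dose, which is two of the five sprays. It adds: "If the dose is reduced during the initial 2-week tolerability period, then subjects will not escalate to the maintenance dose". Protocol 7.14 confirms that reductions for intolerance are permitted.

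For recording, Protocol 10.2.6 states: "Actions taken with respect to investigational agents (discontinuation or not) will also be recorded". The disposition form in Protocol 10.31 has this item: "Subject discontinued investigational products and the reason(s)". It has none for a reduced dose.

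SAP 9.6.1 promises a listing with "action taken (including any treatment administered), and duration will be provided". The shells for Listings 26-28 then fix the codes: "Action Taken Due to AE: 1=None; 2=Treated with Drugs; 3=Non-drug treatment; 4=ER/Outpatient visit; 5=Hospitalization; 6=Referral for treatment". Table 1 counts subjects who discontinue medication. Table 99 covers adverse events leading to discontinuation of the study, and Table 100 is titled "Number and Percentage of Subjects with Adverse Events Leading to Discontinuation of Study Medication". No planned table has a row for reduced dose.

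On compliance, SAP 9.7 and Protocol 11.4.5 divide the amount taken by the total that the protocol prescribes. The footnote to SAP Table 4 divides sprays taken by sprays prescribed in the period.

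**The concern.** Tolerability is a stated secondary objective (Protocol 5.2), and Weeks 1-2 are called the initial tolerability assessment period (Protocol 4.2). One direct result of that period is how many subjects in each arm could not take the assigned dose and were lowered. The planned outputs omit that number, the events that led to each reduction, and the dose level at which subjects entered Week 3.

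Two readings are exposed. A reader who judges tolerability from discontinuations would miss subjects who stayed on drug only at a lower dose. A reader who judges it from compliance would see reductions either as poor adherence or not at all. For the primary endpoint, measured over Weeks 3-12, the report would not state what share of the oxytocin arm never received the maintenance dose, which is useful context for a null result.

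**Working it through.** The plan gives no figure for dose reductions, so there is none to reproduce. The check traces a reduction through the planned records and outputs, then works out what they would display.

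**1. Where a reduction could appear**

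- Adverse event action, Protocol 10.2.6: discontinuation is the only study-drug action named.
- Listings 26-28: six codes, none of them a study-drug action.
- Listing 29 (serious events): yes or no to continued administration.
- Disposition form (Protocol 10.31), Table 1, Tables 99-100: discontinuation only.
- Tables 3-6: sprays or IU taken, and percent compliance.
- Listing 25: monthly volume prescribed and taken by subject, with a reason column for discontinuation only.

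None gives a count of reduced subjects by arm.

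**2. What compliance shows for one reduced subject**

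Inputs from Protocol 6.1: 5 sprays per dose, 7 IU per spray, once daily for 14 days, then twice daily for 70 days.

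- Full regimen: 14×5 + 70×2×5 = 770 sprays (770×7 = 5,390 IU). Protocol 4.1.9 states 5,320 IU. The 70 IU gap (1.3%) should be reconciled but does not affect this point.
- One step down from Week 3: 14×5 + 70×2×3 = 490 sprays.
- Denominator in SAP 9.7: 490/770 = 63.6%.
- Table 4 footnote, if prescribed means the reduced prescription: 490/490 = 100%.
- Full-dose subject missing 40% of maintenance doses: 70 + 0.6×700 = 490 sprays, again 63.6%.

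The first denominator cannot separate a reduction from missed doses. The second hides it.

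**3. What the arm mean shows**

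Assume a share f of the arm is reduced by one step at Week 3 and adherence is otherwise full. Mean compliance on the SAP 9.7 denominator is 1 − f×(1 − 490/770).

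| f | Per-protocol denominator | Reduced-prescription denominator |
|---|---|---|
| 5% | 98.2% | 100% |
| 10% | 96.4% | 100% |
| 20% | 92.7% | 100% |
| 30% | 89.1% | 100% |

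**4. A subject who never escalates**

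Assume one step down on day 8, kept once daily: 7×5 + 77×3 = 266 sprays, or 266/770 = 34.5% of the full regimen. The protocol synopsis describes adverse event summaries by dose, but the split is by calendar weeks (Tables 91-92 and 96-97). This subject's later events therefore fall under Weeks 3-12 with those of subjects on the maintenance dose.

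**5. What a count could show (illustrative rates, 50 per arm)**

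| Oxytocin | Placebo | Fisher p |
|---|---|---|
| 5/50 | 1/50 | 0.20 |
| 10/50 | 2/50 | 0.028 |
| 15/50 | 3/50 | 0.0033 |

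Mean maintenance dose is 70×(1 − f + f×r), where r is the fraction of 70 IU/day that reduced subjects still take. With f = 10% and r = 0.6 (21 IU twice daily) it is 67.2 IU/day. With f = 30% and r = 0.3 (21 IU once daily) it is 55.3 IU/day, the extreme corner of these assumptions.

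**The case against.** The strongest reply is that most of the tolerability evidence survives. An intolerance that prompts a reduction is still an adverse event, tabulated by arm, severity and relationship (Tables 89-98), with Tables 91 and 96 confined to Weeks 1-2. Table 8 compares the arms on side-effect burden and Table 103 on nasal mucosa findings. This stands. A reader might infer that intolerance handled by lowering the dose will simply be reported as good tolerability; those tables do not support that.

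A reader might also infer that reductions go unrecorded. The eCRF is not among the documents, and the parenthesis in 10.2.6 may be shorthand. The Listing 26-28 codes also lack discontinuation, yet Table 100 and Listing 28 depend on it, so that information must come from elsewhere. A missing code in a shell does not prove missing data. The diary holds sprays per dose (Appendix A), telephone calls check actuations (Protocol 7.9), and Listing 25 may show a lowered prescription. This also stands: the count is untabulated, and may be partly derivable.

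Nor would the shortfall vanish from every table. With 20% of oxytocin and 4% of placebo subjects reduced and adherence otherwise full, weekly sprays in Table 3 would average 70×(1 − 0.20×0.4) = 64.4 against 70×(1 − 0.04×0.4) = 68.9 (t-test p = 0.014). Ordinary missed doses would blur that signal, and the table could not say which cause produced it.

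Finally, a reader might infer that a null primary result could not be interpreted. The primary analysis compares the randomized arms in the Full Analysis Set, and SAP 9.7 reports IU per day by arm, weekly and overall. The missing count limits explanation; it does not invalidate the comparison.

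**Conclusion.** The point holds as a reporting gap. Followed as written, the plan produces no count by arm of subjects whose dose was lowered, does not link adverse events to reductions, merges reductions with missed doses or hides them depending on the denominator, and files never-escalated subjects under Weeks 3-12. Tolerability is overstated only to the extent that it is judged from discontinuations and compliance.

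The 63.6% versus 100% contrast follows from the protocol's own regimen for one step down at Week 3. Everything that depends on how many subjects reduce is illustrative, because the documents give no rate; at 5/50 versus 1/50 the difference would not be significant. No endpoint, test or power figure is affected. The change is worth making because it is cheap and serves a stated objective.

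**What to change.** No dosing rule changes.

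- **Recording.** In Protocol 10.2.6, the adverse event eCRF and SAP Listings 26-28, add dose reduced to the coded actions on study drug, alongside discontinued. An interrupted category is optional.
- **Tables.** In Table 1 or Table 100, add by arm the number (%) with any dose reduction, separately for Weeks 1-2 and Weeks 3-12; the adverse events leading to reduction; and the number at full and at reduced dose at the start of Week 3.
- **Compliance.** Reconcile SAP 9.7 with the Table 4 footnote. State which denominator each table uses, so that reductions are not counted as missed doses. One way is to report adherence against the dose prescribed to the subject, and exposure against the full regimen.

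The cost is one extra eCRF code and a few table rows. If the eCRF cannot be changed, the counts would have to be derived from dosing records such as site dosing instructions, diaries and Listing 25 volumes. No visit or procedure is added.
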